5.4 Study Intervention Description

During the Phase 2 of the study participants are randomized into the comparison or intervention arm. Both the comparison and intervention arm participants receive a Fitbit and are asked to complete the interim (between weeks 8-12) and post-intervention (between weeks 20-26) assessments. In addition, the intervention group is asked to complete 8 videoconferencing sessions with a PA coach over 20 weeks (Sessions 1-4 occur weekly; Session 5 is in week 6; Session 6 is in week 8; Session 7 is in week 12; Session 8 is in week 20) with each session lasting approximately 20-30 minutes. Intervention participants who complete the protocol will also be invited to partake in a focus group after the post-intervention assessment has been completed to provide feedback on their study experiences. The topics for the intervention sessions focus on helping participants to:

- 1) Understand the benefits of MVPA, find physical activities they enjoy, and delineate pros and cons of engaging in MVPA using a non-judgmental stance (*Attitudes*)
- 2) Trouble-shoot engaging family and friends to be supportive of or engage in PA with the participant (*Subjective Norms*)
- 3) Find creative ways to incorporate more MVPA, resolve barriers to PA and promote efficacy for engaging in MVPA, and identify intrinsic rewards for accomplishing goals (*Perceived Control*)

All of the sessions contain a goal-setting component based on the exercise prescription the participant obtained from his/her exercise stress test. Participants receive text messages in between sessions, which contain motivational or encouraging content.

5.4.1 Session Description

Session 1 (Week 1)

Coaches inquire about participants' attitudes about PA and encourage them to get familiarized with their Fitbit.

Session 2 (Week 2)

Participants' are encouraged to discuss their knowledge about PA and to think about pros and cons for engaging in PA. Goals are set in collaboration with the participant, including increasing participants' PA frequency, duration, or intensity.

Session 3 (Week 3)

Coaches inquire about participants PA self-efficacy/perceived control by asking what gets in the way of engaging in activities that the participant enjoys and troubleshoot around controllable

barriers. Participants are also encouraged to try a new type of PA. Goals are set for increasing frequency, duration, or intensity when engaging in PA.

Session 4 (Week 4)

Coaches will inquire about participants PA subjective norms (e.g., “Have you talked with your caregivers/siblings/friends/cardiotherapist about being active?” “What do they think about you being active?”), and are encouraged to talk to family/friends/cardiotherapist about being active if they have not, as well as invite family/friends to join them in physical activities. Goals are set to increase frequency, duration, or intensity of PA.

Session 5 (Week 6)

Coaches promote participants’ independence by modeling the use of core concepts from the Theory of Planned Behavior learned in Sessions 1-4 with emphasis placed on managing barriers and promoting boosters to PA. Participants are encouraged to increase frequency, duration, or intensity of PA based on what they perceived as being the easiest to increase.

Session 6 (Week 8)

Coaches continue promoting participants’ independence by discussing the process of goal-setting, including making achievable goals and anticipating barriers. Participants are asked to set up his/her goals in respect to increase frequency, duration, or intensity of PA.

Session 7 (Week 12)

Coaches continue promoting participants’ independence by reflecting about their progress and discussing the process of setting long-term goals. Participants are encouraged to set new goals ever 2 weeks during the span between Session 7 and 8. Coaches help participants identify potential barriers to achieving their goals, as well as how they can continue to use their Fitbit for self-monitoring.

Session 8 (Week 20)

Coaches summarize the intervention, focusing on the participant’s successes and gains. Coaches will also inquire about participants’ motivation and promote maintenance.

5.5 Modification of Study Intervention

Modifications to the study intervention may occur if a participant experiences a change in their cardiac health during the course of the study and his/her cardiotherapist recommends an alteration in the participant’s exercise prescription.

5.6 Accountability Procedures for the Study Intervention

Individual and group supervision sessions are held for coaches to clarify study procedures, receive feedback on interactions with participants, and share ideas for ways to trouble-shoot around barriers to PA that participants broach during session. [name], who is familiar with the study but is not directly involved, as well as another study staff member, will listen to a random selection of 2 audiotaped sessions per participant and rated on their fidelity. Fidelity <90% triggers retraining of the interventionist as to the study materials.

5.7 Assessment of Subject Compliance with Study Intervention

Participant compliance in the intervention arm is monitored in two ways. First, participants are asked to wear a Fitbit, which is used by the coaches to assess the participants' engagement in MVPA. Coaches request that participants in the intervention arm sync their Fitbit each day so that coaches may monitor their PA levels and incorporate feedback during sessions. Participants' attendance at each session is documented. For those participants in the comparison arm, they are told to sync their Fitbit regularly upon first receiving the Fitbit, but are not contacted about the Fitbit again.

5.8 Concomitant Treatments

Given the primary and secondary outcomes of the study, participants who are currently or have engaged in a formal exercise program in the past 6 months, including cardiac rehabilitation, are not able to participate in the study. Engaging in sports during the study is not an exclusionary criterion.

6 STUDY SCHEDULE, STUDY PROCEDURES/ EVALUATIONS

6.1 Screening

Potential participants are identified through scheduled clinic appointments for the upcoming month. Study personnel first identify patients who meet the age criteria and then check the patient's medical record to verify their eligibility based on the inclusion and exclusion criteria. If a patient appears to be eligible the cardiologist confirms that they do not know of any reason the patient should not participate in this research, including limitations to engaging in MVPA. The patient is then sent a letter from the attending cardiologist, notifying them about the study and that study personnel will be in contact.

6.2 Phase 1: Enrollment/Baseline (T1)

Once the participant has consented, they are asked to complete an online questionnaire. The participant is also asked to undergo an exercise stress test and wear an accelerometer for 7 days. The stress test is completed at NCH within 3-4 weeks of recruitment and standardized feedback will be provided by an exercise physiologist, which includes their $VO_{2\max}$. Once completed, participants are compensated \$100 for their time for the baseline assessment.

Baseline online questionnaire:

- Socio-demographics characteristics
- Benefits of PA⁵¹
- Subjective Norms survey⁵²
- Social Support for Exercise survey^{53,55}
- Barriers to Exercise survey⁵⁴
- Self-Efficacy for Exercise Scale⁵⁵
- Patient-Reported Outcomes Measurement Information System⁴⁶⁻⁴⁸
- International Physical Activity Questionnaire^{49,50}
- Cardiac Anxiety Questionnaire⁵⁶
- Modified Body Image Disturbance Questionnaire⁵⁷
- Physical Activity Stages of Change Questionnaire – Algorithm⁵⁸
- Physical Activity Stages of Change Questionnaire - Continuous⁵⁹⁻⁶¹

VO_{2max}: VO₂ measurement is obtained via a graded exercise stress test on a treadmill. Exercise stress test results are used by the exercise physiologist to devise an exercise prescription that consists of recommendations for frequency, duration, intensity and type of PA. Exercise prescriptions are provided to participants if they qualify and enroll in Phase 2. Participants who are found to have an arrhythmia or show evidence of cardiac ischemia during exercise stress testing are immediately referred to their cardiologist for follow-up and are not eligible for Phase 2.

MVPA and SB: Participants receive a triaxial accelerometer (ActiGraph, model wGT3X-BT), sensitive to movement in all directional planes, to measure the amount of time spent in sedentary, light, moderate, and vigorous PA. The accelerometer is worn around the waist for 7 days for at least 10 hours per day, only to be removed when showering or submerging in water (e.g., swimming). Participants will also complete self-monitoring PA logs in the case they cannot wear the accelerometer (e.g. swimming). If baseline accelerometer and self-monitor PA log data indicate that a participant averages at least 150 minutes of MVPA per week, they are not eligible for Phase 2.

Compensation: Participants are compensated \$100 for completing the baseline survey, exercise stress test, and wearing the accelerometer for at least 4 days (1 weekend day, 3 weekdays), for at least 10 hours per day. Additionally, participants' parking and mileage to/from the hospital for the exercise stress test are reimbursed.

Contact and Scheduling. If the participant is eligible for the Phase 2, they are contacted by phone and asked to schedule a home visit, within 8 weeks from their exercise stress test, if interested in participating.

6.3 Phase 2: Enrollment in the RCT

Eligible participants from Phase 1 are met at their home (or the hospital if preferred) to receive their Fitbit and exercise prescription, which is based on the results of their stress test. Home visits may also be conducted virtually (e.g., via Google Hangouts). Participants completing virtual home visits will receive study materials by postal mail or email as appropriate. After receiving the Fitbit and exercise prescription, the participant's arm designation is revealed by opening an envelope that has been prepared by the study statistician, [name]. Prior to opening the envelope, the study PI, study staff, and the participant are blind to the study arm designation.

6.4 Interim Assessment (between weeks 8-12)

Participants in both arms are asked to complete an interim assessment (between weeks 8-12), which includes:

Interim online questionnaire: Participants are asked to complete the same questionnaire that was completed at Baseline, with the exception of those in the comparison arm receiving questions about changes to their health since Baseline.

Benefits of PA⁵¹

Subjective Norms survey⁵²

Social Support for Exercise survey⁵³

Barriers to Exercise survey⁵⁴

Self-Efficacy for Exercise Scale⁵⁵

Patient-Reported Outcomes Measurement Information System⁴⁶⁻⁴⁸

International Physical Activity Questionnaire^{49,50}

Cardiac Anxiety Questionnaire⁵⁶

Changes in Health

Physical Activity Stages of Change Questionnaire – Algorithm⁵⁸

Physical Activity Stages of Change Questionnaire - Continuous⁵⁹⁻⁶¹

MVPA and SB: Participants wear an accelerometer again for the same period (7 days) as the Baseline assessment and complete self-monitoring PA logs in the case they cannot wear the accelerometer (e.g. swimming).

Compensation: Participants are compensated \$50 for completion of the interim assessment survey and wearing the accelerometer for at least 4 days (1 weekend day, 3 weekdays), for at least 10 hours per day.

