6.5 Post-Intervention (between weeks 20-26)

Participants in both arms are asked to complete a post-intervention assessment (between weeks 20-26), which includes:

Post-intervention online questionnaire: Similar items are included on the post-intervention questionnaire as with the baseline and interim assessment with the exception that participants are asked to rate the intervention on multiple dimensions.

Benefits of PA⁵¹

Subjective Norms survey⁵² Social Support for Exercise survey⁵³

Barriers to Exercise survey⁵⁴

Self-Efficacy for Exercise Scale⁵⁵

Patient-Reported Outcomes Measurement Information System⁴⁶⁻⁴⁸

International Physical Activity Questionnaire^{49,50}

Cardiac Anxiety Questionnaire⁵⁶

Changes in Health

Post-Intervention Satisfaction

Physical Activity Stages of Change Questionnaire – Algorithm⁵⁸

Physical Activity Stages of Change Questionnaire - Continuous⁵⁹⁻⁶¹

MVPA and SB: Participants wear an accelerometer again for the same measurement period (7 days) as in previous assessments and complete self-monitoring PA logs in the case they cannot wear the accelerometer (e.g. swimming).

VO_{2max}: VO₂ measurement is obtained again with a graded exercise stress test using a modified Bruce protocol. Participants who were found to have an arrhythmia or show evidence of cardiac ischemia during exercise stress testing will be immediately referred to their cardiologist for follow-up.

Compensation: Participants are compensated \$100 for completion of the post-intervention survey, exercise stress test, and returning the accelerometer with at least 4 days (1 weekend day, 3 weekdays), for at least 10 hours per day of data. Additionally, participants parking and mileage to/from the hospital for the exercise stress test are reimbursed.

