7 ASSESSMENT OF SAFETY

7.1 Methods and Timing for Assessing, Recording, and Analyzing Safety Parameters

7.1.1 Adverse Events

Definition

For the current study, an adverse event is an unanticipated change in cardiovascular, musculoskeletal, or emotional symptoms that are (1) concerning to the participant and (2) results in seeking medical attention, if cardiovascular or musculoskeletal in nature. Any condition that is present at the time that the participant is screened will be considered as baseline and not reported as an adverse event. However, if the study participant's condition deteriorates at any time during the study, it will be recorded as an adverse event. Serious adverse events are defined as adverse events that are severe in classification (as described below). We do not anticipate any serious adverse events due to study procedures. Adverse events that occur for participants during the course of the study are comprehensively documented, including events during the stress test, symptoms reported during the course of the intervention from participants in the intervention arm, dates and reasons for pauses in the study protocol due to symptom reporting, and determination of ability to proceed by participants' cardiologists. All unscheduled cardiology outpatient visits, visits to urgent care or the emergency department, unscheduled hospitalizations, or any other changes in health are documented. Participants in the comparison arm are asked whether they sought medical attention in the aforementioned contexts during the interim and post-intervention questionnaires. Additionally, the occurrence of any adverse event or serious adverse event may come to the attention of study staff during other study contacts (e.g., intervention meetings).

Classification

All adverse events and serious adverse events will be assessed by the PI and the study physician, [name], according to the guidelines outlined here.

Severity: The following guidelines will be used to describe severity:

- Mild: Events require minimal or no treatment and do not interfere with the participant's daily activities.
- Moderate: Events result in a low level of inconvenience or concern with the therapeutic measures. Moderate events may cause some interference with functioning.
- Severe: Events that require in-patient hospitalization and/or resulted in death or permanent disability.

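### 6.4 and 7.1.1 assign the health-change and care-seeking questions to the comparison arm, the 6.4 and 6.5 item lists set no arm limit, and adverse events may therefore be found by different methods in the two arms

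*Combined protocol and SAP*

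**What the plan says.** Section 6.4 describes the interim questionnaire, for both arms, as the baseline questionnaire "with the exception of those in the comparison arm receiving questions about changes to their health since Baseline". The item list beneath that sentence includes "Changes in Health" with no arm label.

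Section 6.5 begins "Participants in both arms are asked to complete a post-intervention assessment (between weeks 20-26". Its list carries the same health-change entry, again with no arm label, and the only exception it states is that participants rate the intervention.

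Section 7.1.1 defines an adverse event as an unanticipated change that concerns the participant and "results in seeking medical attention, if cardiovascular or musculoskeletal in nature". On how events are found, it says:

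- For the comparison arm: "Participants in the comparison arm are asked whether they sought medical attention in the aforementioned contexts during the interim and post-intervention questionnaires".
- For the intervention arm: "symptoms reported during the course of the intervention from participants in the intervention arm".
- With no arm limit: "including events during the stress test", and events that "may come to the attention of study staff during other study contacts (e.g., intervention meetings".
- Also with no arm limit: unscheduled care and other health changes are all documented, but the method of finding them is not given.

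Section 7.5 has the DSMB reports cover adverse events and serious adverse events. They also count participants who contacted their cardiologist over symptoms, and that count is for the treatment arm only.

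**The concern.** Two sections name the comparison arm for the structured questions, and two item lists do not restrict them. Staff who build the questionnaires from the 6.4 sentence and 7.1.1 would leave the items out of the intervention-arm version. Staff who build them from the lists would give the health-change block to everyone.

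Under the first approach, one arm is asked directly about care visits. The other depends on what participants volunteer to a coach or what comes up by chance. Because care-seeking decides whether a cardiovascular or musculoskeletal change counts as an adverse event, the difference affects the definition itself as well as the detail recorded. It also affects serious events: 7.1.1 classes an event requiring in-patient admission as severe, and a direct question would pick up an admission that an unprompted session might not. The halting review in 7.4 depends on unexpected serious events related to the study intervention, so complete capture in the arm that receives coaching matters for oversight.

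**Working it through.** No formula applies, and the plan gives no figure to reproduce. The check sets the sections side by side and counts the stated opportunities to detect an event.

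**1. Which arm is asked, by source**

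| Item and time | Source | Arm stated |
|---|---|---|
| Health change, interim | 6.4 sentence | Comparison |
| Health change, interim | 6.4 list | None stated; assessment is for both arms |
| Health change, post-intervention | 6.5 list | None stated; assessment is for both arms |
| Care-seeking, interim | 7.1.1 | Comparison |
| Care-seeking, post-intervention | 7.1.1 | Comparison |

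The documents do not say whether the care-seeking question is part of the health-change block, so the two are counted separately.

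**2. Structured enquiries per participant**

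- Care-seeking, comparison arm: 1 + 1 = 2.
- Care-seeking, intervention arm, as stated: 0 + 0 = 0.
- Health-change block, comparison arm: 1 + 1 = 2.
- Health-change block, intervention arm: at interim 0 (sentence) or 1 (list). Post-intervention it is 1 by the 6.5 list, or 0 if the comparison-arm wording of 7.1.1 is taken to cover this block as well. The total therefore lies between 0 and 2.

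**3. Whether coach contact, as described, fills the gap**

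- Section 5.4 places the eight sessions in weeks 1, 2, 3, 4, 6, 8, 12 and 20. The gaps are 1, 1, 1, 2, 2, 4 and 8 weeks; the longest is 20 − 12 = 8 weeks.
- No session is scheduled after week 20, so up to 26 − 20 = 6 weeks of the post-intervention window have none.
- None of the eight session descriptions in 5.4.1 mentions asking about symptoms or care visits. The between-session texts in 5.4 are motivational.
- The coach procedure in 2.3.1 and 7.1.1 starts when a participant reports a new cardiac symptom that worries them. It does not extend to musculoskeletal events or to care visits as such.
- The comparison arm has no coach sessions and, under 5.7, no further contact about the Fitbit.

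**4. Other routes**

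The final stress test brings both arms on site, but no event question is stated for that visit. Chart review is described in Section 4 as a source of covariates and moderators, not of adverse events. The cardiologist-contact count in 7.5 captures one form of care-seeking in the treatment arm. It has no counterpart in the comparison arm and does not cover urgent care, emergency visits or musculoskeletal complaints.

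**5. Result**

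Read by the 6.4 sentence and 7.1.1, the comparison arm has a questionnaire and no coach, while the intervention arm has a coach and no stated questionnaire item. The two methods could differ in either direction: eight contacts could bring out more symptoms, and a direct question could bring out more care visits. The documents give no event or capture rate, so the net effect cannot be sized.

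**The case against.** The best defence is that the asymmetry is intended and sensible. Section 7.1.1 first says, for everyone, that unscheduled care and health changes are documented. It then supplies a questionnaire route for the arm that has no coach. On that reading the two routes complement each other. The session descriptions are short topic summaries, and the videoconference worksheets (10.2), the fidelity checklist (Section 9) and the Manual of Procedures (11.5) are not part of these documents. Any of them might contain a symptom or care-visit check. Both item lists also favour equal treatment, and 7.5 shows that the team meant to follow symptom-driven cardiologist contacts in the treatment arm.

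Much of this stands. A reader might infer that intervention-arm participants are never asked about their health. The documents do not support that: 7.1.1 does not say the question is confined to the comparison arm, and the lists carry no restriction. A reader might also infer that harms are under-counted in the coached arm and that the comparison is tilted in its favour. That is unsupported too, because the direction is unknown.

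The defence does not remove the mismatch between the sentence and the list within 6.4, or between 7.1.1 and 6.5. Nor does it make the methods equal: even if coaches do ask, that is a different instrument on a different schedule from the comparison arm's questionnaire.

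It is also fair to say that this is a 40-person feasibility pilot. Safety is not a listed outcome in 3.2, and 7.8 plans no by-arm safety analysis. That limits the weight of the point.

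**Conclusion.** The point holds as a minor one about the completeness and comparability of safety data. The sections disagree on which arm receives the health-change questions, and no structured care-seeking question is stated for the intervention arm, although care-seeking is part of the adverse-event definition. If 6.4 and 7.1.1 are followed as worded, events are found by different methods, and care visits or musculoskeletal events in the coached arm may be missed.

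In size, stated care-seeking enquiries are 2 against 0 per participant, and coach sessions run the other way at 0 against 8 (comparison against intervention). The bias itself has unknown direction and cannot be quantified. No between-arm safety test is planned, and neither the Aim 1 feasibility analysis nor the sample size of 40 is affected. What could be affected is the set of events that reaches the DSMB and any description of events by arm in the pilot report. It would go too far to conclude that the safety data are biased or that the trial's conclusions are at risk.

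This rests on two assumptions: that the 6.4 sentence and 7.1.1 describe what is actually done, and that material outside these documents, such as coach worksheets, does not already supply an equivalent question.

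**What to change.** In 6.4, 6.5 and 7.1.1, state that both arms receive the same existing health-change and care-seeking items at interim and at post-intervention. For each event, record whether it came from the questionnaire or from a coach contact. Any description of events by arm can then use the questionnaire as the common source and show coach-reported events separately, since the difference in coach contact will remain.

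No new instrument is needed. With 40 randomised, about 40 / 2 = 20 intervention-arm participants would answer the items (the protocol also gives about 17 per arm). That is at most 20 × 2 = 40 extra administrations, taking a few minutes per participant, and somewhat more events would have to be logged and classified. If both arms already receive the items, only the wording of the three sections changes.
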